### ***Summative Evaluation of Program Effectiveness***

**Aim 1:** Evaluate the effect of SMAs and SMAs+P2P on diabetes patients' glycemic control, systolic blood pressure, anti-hypertensive use, statin use, and insulin starts at 6 and 12 months post-enrollment.

**Aim 2:** Assess the impact of SMAs and SMAs+P2P on service utilization and patient-centered outcomes at 6 and 12 months post-enrollment.

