#### **5.1.3 Study Population**

##### **VA Patients**

We will enroll up to 1,100 VA patients to the SMA and SMA+P2P groups and 1,100 VA patients to the control group. Inclusion criteria are reflective of the criteria to participate in SMAs and P2P, with the addition of criteria to insure informed consent. Please see section 5.4 for a complete list of these criteria.

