### **Patient Inactive Controls**

Medical record information will be pulled from VA databases. The data will include A1c levels, blood pressures, insulin start dates, statin use, and number of admissions/bed days of care/outpatient visits.

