We will conduct a "difference-in-differences" (DID) analysis on our primary A1c outcome using a multilevel linear mixed effect model. The model will include an indicator of treatment, an indicator for time, the treatment-time interaction (DID estimator), and variables to adjust for baseline A1c, age, gender, and race. Random intercepts to include will be for patients (level-1) nested within site (level-2). An identical analysis will be used for the secondary SBP outcome. In the secondary analyses of insulin and statin starts, we will implement a multilevel logistic regression model, and for anti-hypertensive medication class changes, we will implement a multilevel Poisson regression model. To analyze the 6- and 12-month differences in utilization measures between treatment groups, we will use a two-sample Mann-Whitney U test. Vargha and Delaney's A statistic will be used to describe the effect size of the Mann-Whitney test. As a robustness check, we will repeat the above analyses on a subset of patients who will be matched 1:1 based on propensity scores. The propensity score model will be developed using a logistic regression on the patient demographics. Although our initial analyses will use observed data, because we are relying on data available in the EHR, we anticipate more missing values than if this were an efficacy trial. Accordingly, we will use logistic regression to model patients' likelihood of having outcome data and defined strata within which outcome values were missing at random. We will then stratify patients according to these propensities and randomly sample from the observed outcome distribution and impute these values for missing data within each stratum. As a sensitivity analysis for the primary A1c outcome, we will impute the missing data such that any missing A1c measurements at 6 or 12 months will match the value at baseline.

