Again, we assume that we can conduct 10 to 16 SMA groups per site (equally distributed between SMA and SMA+P2P) with 8-14 people per group. At the maximum, this would give us 1,568 people in active treatment and an equal number of inactive controls. At the minimum, this would give us 560 people in active treatment and an equal number of inactive controls. In this scenario, at our low estimate of 10 SMA groups per site, we can detect an effect size of 5mm decline in SBP with a power of 0.8 across all our ranges of group size and ICC. In this scenario, we also have a power at 0.8 at all estimated ICCs to detect a 0.5% difference in A1c between the active treatment groups and controls.

Table 5 shows a snapshot of the number of eligible patients per site. Across all sites, we will recruit between 560 and 1,568 active treatment patients and an equal number of inactive controls.

**Table 5: Number of Patients with Diabetes\* with qualifying A1c\*\*, and Number of These Patients with and without Serious Mental Illness (SMI) or Substance Use Disorder (SUD) and with SBP>140**

Site	No. of Diabetes Patients	No. of Diabetes Patients without SMI or SUD	No. of Diabetes Patients with Qualifying A1c**	No. with Mean SBP>140 in Past 6 months
West Haven (Firm A)	3,748	306	397	187
Providence	5,466	636	794	105
Palo Alto	3,877	404	534	110
Livermore	1,212	156	168	88
Monterey	3,736	298	381	160
Sacramento	5,847	858	1,045	210
Ann Arbor	11,020	2,064	2,576	955

\*Source: VHA CWD (last updated 2015).

\*\*Patients less than 70 years old with A1c>7.5, for patients age 70 or above Ac1>8.0

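### Utilisation is analysed only by a rank test and a unitless effect size, so for admissions and bed days Aim 2 will say little about how much care was used

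*Combined protocol and SAP*

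**What the plan says.** Aim 2 (section 3.0) is to "Assess the impact of SMAs and SMAs+P2P on service utilization and patient-centered outcomes at 6 and 12 months post-enrollment". Section 5.5, under the inactive controls, lists the utilisation data as "number of admissions/bed days of care/outpatient visits". All three are amounts of care.

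Section 5.6.1 gives one between-group method: "To analyze the 6- and 12-month differences in utilization measures between treatment groups, we will use a two-sample Mann-Whitney U test". It adds that "Vargha and Delaney's A statistic will be used to describe the effect size of the Mann-Whitney test". The only other planned analysis of utilisation repeats the same test in a matched subset: "As a robustness check, we will repeat the above analyses on a subset of patients who will be matched 1:1 based on propensity scores".

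No mean difference, rate ratio, two-part model or count model is named for utilisation. The same paragraph does use count regression for another outcome: "for anti-hypertensive medication class changes, we will implement a multilevel Poisson regression model". No power, effect size or expected level of use is stated for utilisation.

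**The concern.** The Mann-Whitney test and A compare ranks. Their null is that a randomly chosen SMA patient is as likely to rank above a randomly chosen control as below, with ties counted half. That differs from equal mean use per patient. When many patients have a count of zero, most of the rank information lies in who has any use at all, and little in how much they use.

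Two readings of the result could then go wrong. A real fall in bed days through shorter stays, or in admissions through fewer repeats, could be reported as no difference. A difference in ranks could also be read as a change in the amount of care when the mean is unchanged, or has moved the other way. Since A has no unit, it cannot be turned into admissions or bed days per patient.

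**Working it through.** **Inputs from the documents.** The minimum size is 560 per arm (section 5.6.2): "At the minimum, this would give us 560 people in active treatment and an equal number of inactive controls". It is reproduced by 10 groups × 8 people × 7 sites (the rows of Table 5) = 560. The enrolment ceiling is 1,100 per arm (section 5.1.3): "We will enroll up to 1,100 VA patients to the SMA and SMA+P2P groups and 1,100 VA patients to the control group". There is no utilisation figure to reproduce.

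**Assumptions not in the documents.** Two-sided alpha 0.05; independent patients; 10, 15 or 25% of controls with any admission; mean stay 6 bed days among those admitted. The base model for stay is gamma-Poisson. The sensitivity model is lognormal with log-SD 1.5 and the same mean.

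**Step 1: what A measures.** Let p0 and p1 be the shares with any use in control and SMA patients. Let θ be the probability that an SMA user exceeds a control user, with ties counted half. Then

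A − 0.5 = (p1 − p0)/2 + p0·p1·(θ − 0.5).

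The first term is the share with any use. The second, the amount of use, is multiplied by p0·p1.

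**Step 2: weight of the amount when p0 = p1 = p.** Pairs tied at zero: (1 − p)². Any versus none: 2p(1 − p). Both positive: p².

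- p = 10%: 81% tied at zero, 18% any versus none, 1% both positive. At most 1/19 = 5% of untied pairs depend on amount.
- p = 20%: 64%, 32% and 4%; at most 4/36 = 11%.
- p = 30%: 49%, 42% and 9%; at most 9/51 = 18%.

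Even if every admitted SMA patient had fewer days than every admitted control (θ = 0), A = 0.5 − p²/2, which is 0.495, 0.480 and 0.455. If SMAs abolished all admissions (p1 = 0), A = 0.5 − p0/2. At 10, 15 and 25% admitted, that is a shift of 0.05, 0.075 and 0.125.

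**Step 3: rejection rates for bed days by simulation, 560 per arm, at 10 / 15 / 25% of controls admitted.** The comparison of means is a Welch test, a simple stand-in for a bootstrap interval.

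| Scenario | Mann-Whitney | Means |
|---|---|---|
| Same share, stay halved, gamma-Poisson | 5 / 7 / 17% | 76 / 92 / 99% |
| Same share, stay halved, lognormal | not tabulated | 22 / 36 / 61% |
| Equal mean: share × 2/3, stay × 1.5 | 50 / 67 / 87% | about 4 to 6% |
| Share halved, same stay, gamma-Poisson | 90 / 97 / 100% | 66 / 81 / 97% |
| Share halved, same stay, lognormal | 89 / 98 / 100% | 36 / 44 / 60% |

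The third row has equal means because 2/3 × 1.5 = 1. With identical distributions both tests reject about 5% of the time. A larger trial does not close the gap in the first row: at 1,100 per arm and 15% admitted, the figures are 8% against 99.6%.

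**Step 4: direction.** Take 20% of controls admitted for a mean of 6 days, against 30% of SMA patients for 3.5 days. Mean days per patient fall from 0.20 × 6 = 1.20 to 0.30 × 3.5 = 1.05, yet A is 0.541, which points to higher use.

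**Step 5: other measures and readings.** For admissions, with the same share admitted and the mean per admitted patient falling from 1.8 to 1.3, Mann-Whitney rejects 5 / 6 / 12% of the time at 10 / 20 / 30% admitted, against 32 / 60 / 81% for means. For outpatient visits, with an assumed mean falling from 10 to 8.5, it is 79% against 86%, so the rank test does adequately. If the planned differences are changes from baseline, the gap narrows but remains: for bed days down one third, 5 / 8 / 15% against 16 / 35 / 49% at 10 / 20 / 30% admitted.

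**The case against.** A rank test with A is a recognised choice for skewed counts, and several objections to the concern stand.

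- The share with zero use is assumed. The documents give no admission rate or length of stay.
- The scenarios that hurt the rank test are chosen patterns. A self-management programme could as plausibly change whether patients are admitted, and there Mann-Whitney is clearly better.
- The advantage of comparing means depends on the tail of the stay distribution. With the lognormal tail it falls to 22 to 61%.
- Utilisation is not the primary outcome. The adoption threshold that section 5.6.2 attributes to clinical managers concerns A1c and systolic blood pressure, and Aim 4 costs only the P2P programme itself.
- The plan is brief and does not rule out descriptive means or percentages.

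A reader might also infer that the test manufactures false positives. It does not. In the equal-means scenario the two distributions really differ, so rejection is correct for the rank hypothesis; the mismatch is with the question about amount.

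What these objections leave untouched is Steps 1 and 2, which follow from the definition of A for any share with zero use and any stay distribution, and the fact that no estimate in units of care is planned.

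**Conclusion.** The concern holds in a limited form. For admissions and bed days, and provided most patients have none in 6 to 12 months, the planned analysis mainly compares the share with any admission and does not address mean use per patient. At 560 per arm and 10 to 25% admitted, it detects a halved stay about 5 to 17% of the time. The comparison of means reaches about 76 to 99% with gamma-Poisson stay and about 22 to 61% with a heavy lognormal tail. All these rates rest on the assumptions listed, including independence within SMA groups.

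Two stronger readings are not supported. One is that Aim 2 as a whole is compromised: outpatient visits are probably not mostly zero, and the survey outcomes are analysed separately. The other is that Mann-Whitney should be dropped or demoted for all three measures: it is valid under identical distributions and the more powerful choice when only the share admitted changes. What applies to all three measures is that A has no unit. This is a low-cost improvement to a non-primary outcome.

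**What to change.** In section 5.6.1, keep the Mann-Whitney test and A, and add for admissions and bed days at 6 and 12 months:

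1. the between-group difference in mean use per patient, or the rate ratio, with a 95% confidence interval (bootstrap within site, or a negative binomial model with robust variance);
2. the share of patients with any admission in each arm.

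State that conclusions about the amount of care used rest on item 1. For outpatient visits, report the mean difference with a 95% confidence interval beside A.

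The cost is a few sentences in the plan and a few lines of code; no new data are needed. The downsides are wide intervals for skewed counts and a few more secondary estimates.

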### **Prior P2P Efficacy Trial**

The proposed pragmatic clinical trial will extend findings from [name] et al.'s RCT comparing a reciprocal peer support program (P2P) with a nurse care management model (NCM) funded through an HSR&D IIR (04-239). Patients in the P2P group attended an initial group session to set diabetes-related behavioral goals, receive peer communication skills training, and be paired with another age-matched peer in the same cohort of study participants. Both peers had poor glycemic control and were encouraged both to give and receive support from each other in their joint efforts to improve glycemic control. Peers were encouraged to talk weekly using a telephone platform that recorded call occurrence

and provided reminders to promote peer contact. Optional group sessions were offered at 1, 3, and 6 months. NCM patients attended an initial educational session, were assigned to a nurse manager, and were helped to make follow-up appointments with that NCM.

The 244 participants were from 2 VA health care facilities and had A1c levels greater than 7.5% during the 6 months prior to enrollment. In the 216 patients (89%) who completed the A1c assessments at 6 months, mean A1c level decreased from 8.02% to 7.73% (-0.29%) in the P2P group and increased from 7.93% to 8.22% (+0.29%) in the NCM group (between-group difference 0.58%,  $P = 0.004$ ). Among patients with a baseline A1c level  $>8.0\%$ , those in the P2P group had a mean decrease of 0.88%, compared with a 0.07% decrease among those in the NCM group (between-group difference, 0.81%;  $P < 0.001$ ). Eight patients in the P2P group started insulin therapy, compared with 1 patient in the NCM group ( $P = 0.020$ ). Patients in the P2P program expressed high levels of satisfaction with their participation. While this RCT examined P2P as a stand-alone program, its design is well-suited to complement and extend formal professional-led programs such as diabetes SMAs, as is proposed in the current application.

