We will use a mixed methods approach to our data collection and analyses. Summative data for Aims 1 and the service utilization outcomes in Aim 2 will be obtained from VA databases and will include data on clinical outcomes and service utilization, which will be measured at baseline, at 6 months, and over a period of 12-18 months post-enrollment. Because this is an implementation study, we intend to use clinical data wherever possible, rather than add to staff burden with the imposition of additional collection of data solely for research purposes—especially when data on the clinical measures of interest are already collected as part of patient care. For two of the arms (SMA, SMA+P2P), we expect labs to be drawn at baseline and 6 months through SMA staff as part of usual care. In usual care without SMAs, we may have more missing values for A1cs, although guidelines recommending checking A1cs at least every 6 months in patients with poor glycemic control.

Data on patient-centered outcomes (Aim 2) will be obtained from surveys of all participants who are scheduled to participate in SMAs and agree to participate in the study at the five sites to allow for comparisons across the SMA and SMA + P2P groups. We will collect laboratory and service utilization data on patients in all three treatment groups. Qualitative data on organizational factors likely to affect P2P program implementation will be obtained via semi-structured interviews prior to implementation, mid-implementation (7-10 months following program implementation at each site), and post-implementation (18-24 months following program implementation at each site) as part of Aim 3. To further look into the SMA sustainment efforts in Ann Arbor, additional staff interviews, staff meeting observations, and SMA observations will be conducted in Ann Arbor only. Data on staff time required for implementation of P2P will also be collected throughout the study to calculate the overall cost of program implementation (Aim 4).

Patient enrollment will take place for 18 months at the five sites. Patients receiving P2P can stay in the P2P program as long as they wish (while the program is being funded).

VA patient research procedures include completion of three surveys (baseline, 6 months post-enrollment, and 12 months post-enrollment) and collection of medical record data from VA databases. Additionally, a subset of participants will be asked to participate in interviews as part of the program evaluation.

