We present sample size calculations using Satterthwaite's approximate F test using modified degrees of freedom rather than a t-test to calculate the power for trials and the number of clusters and cluster sizes required for the difference of means in the presence of clustering or differential clustering effects between study arms as described by Roberts (2005) and implemented by Batistatou and Roberts (2011). We estimate that we can conduct 10 to 16 SMA groups per site (equally distributed between SMA and SMA+P2P) with 8-14 people per group. At our low estimate of 10 SMA groups per site, we can detect an effect size of 0.5% decline in A1c with a power of 0.8 for all but the lowest number of participants per group (10) and highest ICC (0.1).

For the comparison of both SMA groups to inactive control we must take into account the differential ICC between groups as the inactive controls will have no clustering induced by the treatment and therefore will have an ICC of 0. We continue to assume a worst case scenario of an ICC of 0.10 in the intervention group. In this case we examine our ability to detect a difference of 5mm Hg in blood pressure between SMA groups and the inactive controls.

The standard deviation of a decline in A1c was estimated to be 1.45 from this same RCT mentioned in the paragraph above. The estimate of the standard error of the change in BP was estimated from a database of actual BPs obtained in routine clinical practice for 24,000 patients with diabetes and hypertension in one large service network in the VA over a 24 month period in FY 2004-2005. It depends on both the variation in BP change at the person level and variability within person between measurements. Increasing numbers of measurements in the 6 month window decreases the within person component of variance. Using the proposed 6 month pre- and post-intervention windows on either side of a 12-month intervention period we estimated the standard error for the change in blood pressure as 17 mmHg for the mean of 3 BP measurements that was observed in the sample for each of the pre and post periods.

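### The supporting imputed analysis fills each missing outcome with one random draw from response-propensity strata, with no donor restriction by arm or baseline A1c and no repeated draws or variance rule

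*Combined protocol and SAP*

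**What the plan says.** Section 5.6.1 (Aim 1) puts an analysis of available data first: "Although our initial analyses will use observed data". Because more values are expected to be missing than in an efficacy trial, it then fits a logistic model for having outcome data, and speaks of "defined strata within which outcome values were missing at random". Within those strata it will "randomly sample from the observed outcome distribution and impute these values for missing data within each stratum". One draw is described. The predictors in the response model, the number of strata, the arm of the donors, the number of draws and the variance calculation are not stated there or elsewhere.

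The A1c model itself contains treatment, time, their interaction and "variables to adjust for baseline A1c, age, gender, and race". The only propensity predictors that the section names belong to the separate 1:1 matching: "The propensity score model will be developed using a logistic regression on the patient demographics". For A1c there is one further sensitivity analysis, which sets a missing 6- or 12-month value equal to baseline.

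Section 5.1.1 warns that missingness may differ by arm: "In usual care without SMAs, we may have more missing values for A1cs".

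**The concern.** A draw from a stratum reproduces that stratum's outcome distribution. It does not reproduce the difference between arms inside the stratum unless the donors come from the patient's own arm. With pooled donors, some SMA patients receive usual-care values and the reverse, and the estimated effect moves toward zero.

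Restricting donors to the same arm cures this but exposes a second gap. A single set of drawn values, analysed as if observed, adds random noise to the estimate that the model's standard error does not count.

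A third gap concerns baseline A1c. If usual-care patients have missing follow-up because of their baseline level, and the strata ignore it, the drawn values come from patients with a different baseline.

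The imputed analysis is the plan's stated answer to missing health-record data. If it disagreed with the observed-data result, a reader could not tell whether the missing data or the filling rule was the cause.

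**Working it through.** The plan attaches no figure to this procedure, so there is none to reproduce. The check uses a closed form and a simulation.

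**Inputs from the documents.** Section 5.6.2: at least 560 per arm, an A1c effect of 0.5, and "The standard deviation of a decline in A1c was estimated to be 1.45". Section 2.6, on the prior trial: "In the 216 patients (89%) who completed the A1c assessments at 6 months", so about 11% were missing (28 of 244).

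**Assumptions.** All other missing rates; baseline-to-follow-up correlation 0.5; five strata; one demographic covariate predicting missingness with log-odds 0.3 per SD (range 0 to 0.6) and unrelated to outcome; 1,000 runs per setting; independent errors. Rates are SMA / usual care.

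**1. Pooled donors.** Let fT and fC be the missing shares and dT = (1-fT)/[(1-fT)+(1-fC)] the share of donors from SMA. If strata are unrelated to arm, the share of the effect kept is 1 - fT(1-dT) - fC·dT. For 10/20: dT = 0.9/1.7 = 0.529, and 1 - 0.10×0.471 - 0.20×0.529 = 0.847, so -0.50 becomes -0.424.

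| Missing % | Share kept | Closed form | Simulated, arm not in response model | Simulated, arm in response model (log-odds 0 to 0.6) |
|---|---|---|---|---|
| 10/10 | 0.900 | -0.450 | -0.45 | -0.48 to -0.45 |
| 11/11 | 0.890 | -0.445 | -0.45 | -0.47 to -0.44 |
| 30/30 | 0.700 | -0.350 | -0.35 | -0.42 to -0.35 |
| 10/20 | 0.847 | -0.424 | -0.42 | -0.49 to -0.45 |
| 15/35 | 0.737 | -0.368 | -0.37 | -0.48 to -0.45 |

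At log-odds 0 with equal rates, data are missing completely at random and the shrinkage remains. With no true effect, pooled draws at 15/35 gave a type I error of 4%. Correlation within SMA groups (ICC 0.10, groups of 10) left the 15/35 estimate at -0.37.

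**2. Within-arm donors, one draw.** For a plain comparison of follow-up means, the filled arm mean has variance (σ²/n)·[1/(1-f) + f], while the analysis assumes σ²/n. At 15% the bracket is 1.326 and at 35% it is 1.888; the average is 1.607. The model standard error is then 1/√1.607 = 0.789 of the true one. The nominal 5% test uses an effective cut-off of 1.96×0.789 = 1.546, an error rate of about 12%.

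The simulation of a baseline-adjusted analysis agrees:

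| Missing % | Model SE | True SE | Coverage |
|---|---|---|---|
| 10/10 | 0.077 | 0.083-0.085 | 93% |
| 15/35 | 0.080 | 0.097-0.104 | 87-90% |
| 30/30 | 0.081 | 0.109-0.113 | 83-86% |

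Type I error at 15/35 was about 12%. A difference-in-differences on change suffers less: coverage 94%, 91-94% and 89-90% at the three rates, and type I error about 7% at 15/35.

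**3. Usual-care missingness tied to baseline A1c** (log-odds 0.5 per SD, 15/35, within-arm draws). Estimates when low-baseline / high-baseline controls are missing more often:
- response model omits baseline: -0.62 / -0.38;
- baseline added, no interaction: -0.56 / -0.45;
- arm-by-baseline interaction added: -0.52 / -0.48.

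**4. Replacement.** Multiple imputation by arm on baseline, 20 imputations: -0.49 to -0.50 in all settings, coverage 93-96%.

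**The case against.** **The text does not say that donors cross arms.** True. The response model's predictors are unlisted, and the demographics sentence concerns matching only. Pooled shrinkage and single-draw undercoverage are therefore branches of an unspecified rule. A reader might add the two harms together. That is wrong: the undercoverage is quantified for within-arm draws, and pooled draws on demographic strata did not inflate type I error.

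**The unequal-rate figures break the plan's own condition.** This stands. If arm predicts both missingness and outcome and is left out of the strata, values are not missing at random within them. With arm and the demographic covariate in the response model, the estimates are about -0.45 to -0.49. Only the equal-rate rows show shrinkage with the condition met. Adding baseline A1c as well, with donors still pooled, gives no stable answer: about -0.31 to -0.59 over the settings tried, depending on how missingness relates to baseline and arm.

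**The large figures rest on assumed rates.** This also stands. The one documented rate, 11% in the prior trial, gives a loss of about 0.05.

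**The primary result is untouched.** A reader might infer that the main A1c result is biased. The documents do not support that, because the observed-data analysis does not use the rule. Nor does this point show that the planned observed-data model is sound. Under baseline-dependent usual-care missingness at 15/35, a random-intercept difference-in-differences that also carried baseline A1c as a covariate gave about -0.43 or -0.57, depending on direction; without that covariate it gave about -0.50.

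**Conclusion.** The point holds for the supporting imputed analysis only. Both ways of choosing donors have a defect. Pooling shrinks a real effect: slightly at the prior trial's missing rate, and by 30% of its size at an assumed 30% missing in both arms. Within-arm draws used once give intervals that are too narrow. If the strata also ignore a link between baseline A1c and usual-care missingness, the bias can go either way.

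The sizes depend on the assumed missing rates, correlation, covariate strength and five strata. Coverage under clustering was not assessed, and only A1c was simulated, although the rule is worded for outcomes generally. The plan should be changed, but this does not threaten its first analysis.

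**What to change.** Replace the single draw with multiple imputation (for example 20 or more imputations), done separately by arm. Condition on the baseline value of the outcome concerned (A1c for A1c, SBP for SBP), site, age, gender, race and the response-model predictors, with a model suited to each outcome type. Combine by Rubin's rules, and list the response-model predictors in the plan.

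If the strata are kept, put arm, baseline and their interaction in the response model, draw donors within arm, and repeat and pool the draws. At 15/35 this restored coverage to 95-96%, with a larger standard error than multiple imputation (0.096 against 0.088).

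The cost is SAP wording and routine programming, with no new data. Intervals are slightly wider than with one draw (SE about 0.088 against 0.080 at 15/35). Multiple imputation performed well partly because it matched the model that generated the simulated data. It should not be expected to add precision: the observed-data regression in the same simulation had a standard error of 0.087.

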## 5.4 Inclusion/Exclusion Criteria

### **VA Patients**

Inclusion criteria are reflective of the criteria to participate in SMAs and P2P, with the addition of criteria to insure informed consent:

1. Meet at least one of the following criteria in the past 2 years:  
For data pull patients:
  - a. At least one VA hospitalization with a type 2 diabetes-related ICD-9 or 10 code
  - b. At least two VA outpatient visits with a type 2 diabetes-related ICD-9 or 10 code, or
  - c. At least one VA prescription for a glucose control medication (insulin or oral agents) or monitoring supplies.  
For clinical referrals:
  - a. Scheduled for diabetes SMA
2. Poor glycemic control, indicated by a HbA1c in the past six months of:
  - a. at least 7.5% if age < 70, or
  - b. at least 8% if age 70+
3. No active substance abuse disorder (smoking cigarettes is not an exclusion)
4. No serious psychiatric illness, including bipolar disorder, dementia, schizophrenia, or personality disorders (MDD and PTSD are not exclusions)
5. Has a current address and telephone number listed in VA databases
6. Is competent to provide informed consent
7. Can communicate in English and by telephone
8. Not terminally ill
9. Able to participate in an outpatient program
10. Not a prisoner

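### The only check on departures from missing at random for A1c sets missing values to baseline, which is not a conservative bound and overstates precision

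*Combined protocol and SAP*

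**What the plan says.** Section 5.6.1 (Aim 1) treats missing A1c in three layers. The main model uses observed data. Response propensity is then modelled, patients are stratified on it, and the plan will "randomly sample from the observed outcome distribution and impute these values for missing data within each stratum", on the premise that data are missing at random within strata. Last comes the single analysis that the plan labels as testing sensitivity, and its rule reads: "we will impute the missing data such that any missing A1c measurements at 6 or 12 months will match the value at baseline".

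The same section also says "we will repeat the above analyses on a subset of patients who will be matched 1:1 based on propensity scores". That robustness check deals with differences between the groups, not with missing A1c. No shifted, tipping-point or other missing-not-at-random analysis is named.

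Three other places bear on the rule:

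- Section 5.1.1 on the two SMA arms: "we expect labs to be drawn at baseline and 6 months through SMA staff". On controls: "In usual care without SMAs, we may have more missing values for A1cs". It adds that guidelines advise six-monthly A1c checks in such patients. No missing rates are given.
- Section 5.4 selects on "Poor glycemic control, indicated by a HbA1c in the past six months of" at least 7.5% (under 70) or at least 8% (70 and over).
- Section 2.6, on the prior efficacy trial, reports that mean A1c "increased from 7.93% to 8.22% (+0.29%) in the NCM group". In patients with a baseline above 8.0%, that arm fell by 0.07%.

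**The concern.** Filling with baseline is often defended as cautious because it seems to pull the treatment effect towards zero. That holds when the untreated change is zero or the arms miss equally. Neither can be taken for granted here. Patients enter on a raised A1c, so some drift is plausible whether or not they attend SMAs. Controls may also miss more, because SMA staff arrange laboratory tests only in the SMA arms. The artificial zero could then fall on a larger share of controls and remove the natural change unequally.

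The filled values also carry no variability, so the analysis looks more precise than it is. At stake is whether the one analysis meant to test departures from missing at random can bear that interpretation. It may disagree with the primary result for reasons unrelated to the effect of SMAs, or agree with it without having tested anything.

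**Working it through.** **Inputs from the documents.** SD of A1c change 1.45; minimum 560 in active treatment and 560 controls; planning difference 0.5%; worst-case ICC 0.10 in the SMA arm and 0 in controls (all section 5.6.2). Comparison-arm changes of +0.29 and −0.07 come from section 2.6.

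**Assumed.** Two-sided 5% test; missingness unrelated to outcome within arm; missing rates of 15 to 35%; natural changes of −0.2 and −0.4. The test is a simple comparison of mean change, not the full planned mixed model.

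**Plan's own figures.** 7 sites (as listed in Table 5) × 10 groups × 8 people = 560. (The text of 5.6.2 counts 8 sites, which would give 640.) With ICC 0.10, SE = 1.45 × √((1 + 7 × 0.10)/560 + 1/560) = 0.101, and power for 0.5% is about 0.999. The stated 0.8 therefore holds as a lower bound.

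**Bias.** Let mS and mC be the fractions missing, and dS and dC the true mean changes. The filled estimate is (1 − mS)dS − (1 − mC)dC, so

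bias = mC·dC − mS·dS.

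With no true effect (dS = dC = d) this is (mC − mS)d. It vanishes only if d = 0 or the arms miss equally.

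**Standard error.** The variance of a filled arm is (1 − m)·1.45² + m(1 − m)d². At mS = 0.15, mC = 0.35 and d = −0.4:

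- SMA: 0.85 × 2.1025 + 0.1275 × 0.16 = 1.808
- Control: 0.65 × 2.1025 + 0.2275 × 0.16 = 1.403
- SE = √((1.808 + 1.403)/560) = 0.076

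The observed-data SE is 1.45 × √(1/476 + 1/364) = 0.101. With no data missing at all it would be 1.45 × √(2/560) = 0.087. The filled analysis thus claims more precision than complete data would give.

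**Rejection rate with no true effect** (normal approximation, no clustering):

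| Missing SMA / control | Natural change | Estimate | SE | Rejection |
|---|---|---|---|---|
| 15% / 35% | −0.07 | −0.014 | 0.075 | 5.4% |
| 15% / 35% | −0.2 | −0.040 | 0.075 | 8.3% |
| 15% / 35% | −0.4 | −0.080 | 0.076 | 18.4% |
| 15% / 35% | +0.29 | +0.058 | 0.075 | 12.0% |
| 15% / 25% | −0.4 | −0.040 | 0.078 | 8.1% |
| 20% / 25% | −0.4 | −0.020 | 0.077 | 5.8% |

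A negative estimate favours SMA. Simulations of 8,000 trials for the 15%/35% rows and the 15%/25% row agree to within about a percentage point. With ICC 0.10 and a cluster-level standard error, the 18.4% becomes about 15%.

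**With a true effect of −0.5** and 15%/35% missing, the filled estimate depends on the control change:

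- −0.4: 0.85 × (−0.9) − 0.65 × (−0.4) = −0.505
- −0.07: 0.85 × (−0.57) − 0.65 × (−0.07) = −0.439
- +0.29: 0.85 × (−0.21) − 0.65 × 0.29 = −0.367

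The same rule may therefore leave the effect unchanged or shrink it by about a quarter.

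**The case against.** The strongest reply is that this is the third of three layers. The stratified imputation already addresses missing A1c. If missingness is unrelated to outcome within arm, the observed-data estimate is unbiased, so a distorted third layer would visibly disagree with a sound primary result. This stands: the primary estimate is not in question.

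The inputs are also uncertain. Section 5.1.1 says only that controls may miss more, and cites guideline testing that would limit the gap. SMA-staff laboratory tests are mentioned only at baseline and 6 months, so no reason is given for a gap at 12 months. The intention-to-treat SMA group includes people who never attended and may lack those tests. A narrower gap nearly removes the problem, as the 20%/25% row shows. The documents' only trend figures are +0.29, which works against SMA, and −0.07, which leaves the error rate essentially nominal. That comparison arm received nurse care management, so it is an imperfect guide to usual care. This stands too, and it is why a range is shown.

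A reader might infer that the −0.505 result shows the rule falsely confirming robustness. It does not: in that scenario the observed-data answer of −0.5 is already correct, and the match is a near-cancellation (0.35 × −0.4 = −0.140 against 0.15 × −0.9 = −0.135).

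What does not stand is any defence of the rule as conservative. The sign of its bias is unknown in advance, and its standard error is too small.

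**Conclusion.** The concern holds in a limited form. Carrying baseline forward is the plan's only named check on departures from missing at random. It is not a conservative bound, and it overstates precision (SE about 0.076 against 0.101 at 560 per arm with 15%/35% missing). Across the inputs shown, its bias with no true effect runs from −0.08 to +0.06, small beside the 0.5 planning difference. Rejection lies between about 5% and 18% in place of 5%. These figures depend on assumed missing rates, on natural changes of which only −0.07 and +0.29 come from the documents, and on missingness unrelated to outcome within arm.

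Two stronger readings are tempting and unsupported. One is that the plan has no other handling of missing A1c; it has the stratified imputation. The other is that the trial would report a spurious SMA benefit; the primary analysis is unaffected, and the documents do not establish the sizeable usual-care fall which that would need. The risk is a misleading sensitivity result. A change is worth making before analysis, but it is not critical.

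**What to change.** In section 5.6.1, make the named sensitivity analysis a multiple imputation of missing 6- and 12-month A1c given baseline A1c and arm. Add fixed shifts to the imputed values separately in the SMA and control arms over a stated grid, and report the combinations at which the conclusion changes (a two-way tipping point). Both arms must vary, because the possible excess of missing values is in the controls. A control-based version for SMA patients could be added as an option. Report the fraction missing by arm and visit beside it.

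If carrying baseline forward is kept, label it descriptive and do not present it as evidence of robustness.

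The cost is a paragraph of SAP text and modest programming, with no new data. The price is wider intervals and possibly a somewhat smaller estimate.
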